7.5 Interim monitoring guidelines

We have not planned for formal interim analyses for efficacy and therefore there are no stopping rules for efficacy for this trial. This is a 'proof of concept', early Phase II trial which will be useful in supporting future studies of the intervention even if null.

7.6 Protocol violations

Serious protocol violations such as discontinuation of experimental treatment unrelated to AEs will be carefully recorded and regularly reviewed by the lead study investigators Drs. [name] and [name]. Remedial changes in procedure will be recommended where feasible to reduce the incidence of such violations. The causes and circumstances of all violations will be documented where known for purposes of future secondary analyses and interpretation. Because all primary analyses will be intent-to-treat, it is essential that violations be kept to a minimum especially where it is possible to influence their rate of occurrence.

7.7 Safety and masking analysis

All subjects will be assessed for toxicity and included in the safety analysis. This analysis will include summaries of the incidence and grade of toxicities. Safety interim analyses will be performed and reported to the DSMB. Subjects will be evaluated for SAEs.

Chapter 8. Quality Control

Design strategies and monitoring activities throughout the study will ensure the integrity and high quality of the data. Design strategies include randomization of treatment assignment, masking, and training and certification of personnel. The rigorous monitoring program includes data queries and performance monitoring over the time of the trial.

8.1 Personnel training

Prior to randomization of the first subject in the study protocol, the lead investigators will ensure that staff has completed appropriate training and that all documentation including IRB approval is completed and available. The purpose of training is to ensure that study personnel are carrying out the protocol in a consistent way and are adhering to good clinical practice guidelines. Staff will have current Human Subjects Training Certification on file. Before enrollment begins, study coordinators and research assistants who will perform the outcome assessments will be trained in all procedures, including completion of case-report forms (CRFs).

The lead investigators and research staff will constitute the first line of monitoring of the safety of the human participants. Surveillance for AEs will consist of questioning subjects about potential AEs at every study contact, having subjects report any adverse event to the study team, and having subjects undergo vital sign checks and physical exams during each study visit. Laboratories will be performed at designated visits and checked.

All study personnel are required to read the consent form, the protocol and the manual of procedures (MOP).

8.2 Data quality

The lead investigators, Drs. [name] and/or [name], will perform continuous monitoring of data quality and completion of CRFs.

Periodic audits will be conducted. The research staff will review database forms and source documents to ensure that the information on the forms is complete and consistent with the source documents. All consent forms and screening logs will be audited.

Chapter 9. Participant Safety and Confidentiality

9.1 Consent

Written consent will be obtained for enrollment from participants. For each consent process, study personnel will discuss the details of the study, the risks and benefits, and the subject's rights and responsibilities if they choose to participate in the trial and their right to refuse to participate. It will be made clear that their clinical care will not be affected by their decision. Subjects will be permitted to provide verbal consent over the phone prior to being scheduled for a baseline visit. A consent script will be provided and documentation of verbal consent will be noted. When the subject arrives for the baseline visit, written consent will be obtained.

9.2 Institutional Review Board (IRB) process

The Vanderbilt University Medical Center IRB program will be the approving IRB for this study, and its maintenance.

9.3 Laboratory values

The following clinical laboratory tests will be measured at baseline.

9.3.1 Hematology

Complete blood count, including hemoglobin, hematocrit, and platelets.

9.3.2 Chemistry

Basic metabolic panel including blood urea nitrogen, creatinine, and calcium.

9.3.3 Liver Function Tests

Hepatic panel including alanine aminotransferase, aspartate aminotransferase, total bilirubin and albumin.

9.3.4 Coagulation Studies

Prothrombin time, international normalized ratio (INR).

9.3.5 Cardiac-related

BNP level.

9.3.6. Urine

Urine will be performed.

9.3.7. Pregnancy Testing

Serum HcG

9.4 Safety and Adverse events

9.4.1 Definitions of Adverse Events

9.4.1.1 Adverse Event

An adverse event (also known as an adverse experience) is defined as any untoward medical occurrence associated with the use of a drug in humans, whether or not considered drug related. More specifically, an adverse event (can be any unfavorable and unintended sign (e.g., an abnormal laboratory finding), symptom, or disease temporally associated with the use of a drug, without any judgment about causality. An adverse event can arise from any use of the drug (e.g., off-label use, use in combination with another drug) and from any route of administration, formulation, or dose, including an overdose.

Adverse event (AE): Any symptom, sign, illness or experience that develops or worsens in severity during the course of the study. Intercurrent illnesses or injuries should be regarded as AEs. Abnormal results of diagnostic procedures are considered to be AEs if the abnormality:

- results in study withdrawal
- is associated with a serious AE
- is associated with clinical signs or symptoms
- leads to additional treatment or to further diagnostic tests
- is considered by the investigator to be of clinical significance

9.4.1.2 Serious adverse event (SAE): Adverse reactions are classified as serious or non-serious. A **serious adverse event** is any AE that is:

- fatal
- life-threatening
- requires or prolongs hospital stay
- results in persistent or significant disability or incapacity
- a congenital anomaly or birth defect
- an important medical event

Events **not** considered to be serious adverse events are hospitalizations for:

- routine treatment or monitoring of the studied indication, not associated with any deterioration in condition, or for elective procedures
- elective or pre-planned treatment for a pre-existing condition that did not worsen
- emergency outpatient treatment for an event not fulfilling the serious criteria outlined above and not resulting in inpatient admission
- respite care

Important medical events are those that may not be immediately life threatening, but are clearly of major clinical significance. They may jeopardize the subject, and may require intervention to prevent one of the other serious outcomes noted above. For example, drug overdose or abuse, a seizure that did not result in in-subject hospitalization or intensive treatment of bronchospasm in an emergency department would typically be considered serious.

All AEs that do not meet any of the criteria for serious should be regarded as **non-serious AEs**.

9.4.1.3 Adverse reaction

An adverse reaction is defined as any adverse event caused by the use of a drug. Adverse reactions are a subset of all suspected adverse reactions for which there is reason to conclude that the drug caused the event.

9.4.1.4 Suspected adverse reaction: is any adverse event for which there is a reasonable possibility that the drug caused the adverse event. For reporting purposes, "reasonable possibility" means there is evidence to suggest a causal relationship between the drug/investigational product and the adverse event.

9.4.2. Classifying AEs

Severity of the AE

The intensity of the AE is classified according to the CTCAEv4.0 (https://evs.nci.nih.gov/ftp1/CTCAE/CTCAE_4.03_2010-06-14_QuickReference_5x7.pdf) Grade refers to the severity (intensity) of the AE:

If the intensity of an AE worsens during study drug administration, only the worst intensity should be reported on the AE page. If the AE lessens in intensity, no change in the severity is required.

CTCAEv4 Grade 1: mild; asymptomatic or mild symptoms; clinical or diagnostic observations only; intervention is not indicated.

CTCAEv4 Grade 2: moderate; minimal, local, or noninvasive intervention is indicated; limiting to age-appropriate instrumental activities of daily living (ADL; instrumental ADL refers to preparing meals, shopping for groceries or clothes, using the telephone, managing money, etc).

CTCAEv4 Grade 3: severe or medically significant but not immediately life threatening; hospitalization or prolongation of hospitalization is indicated; disabling; limiting to self-care ADL (self-care ADL refers to bathing, dressing and undressing, feeding self, using the toilet, taking medications, and not bedridden).

CTCAEv4 Grade 4: life-threatening consequences; urgent intervention is indicated.

CTCAEv4 Grade 5: death due to an AE.

In this grading system, severity is not equivalent to seriousness. For example, a SAE would be any event which was life-threatening or disabling (Grade 4) or fatal (Grade 5) or was moderate-severe (Grade 2-3) and required or prolonged hospitalization.

9.4.3 Expectedness

AEs must be assessed as to whether they were expected to occur or were unexpected, meaning not anticipated based on current knowledge found in the protocol, investigator brochure, product insert, or label.

Expected: an AE known to be associated with the intervention or condition under study.

The Office of Human Protections (OHRP) (<https://www.hhs.gov/ohrp/>) defines an **unexpected AE** as any AE occurring in one or more subjects participating in a research protocol, the nature, severity, or frequency of which is **not** consistent with either:

- 1) the known or foreseeable risk of AEs associated with the procedures involved in the research that are described in a) the protocol-related documents, such as the IRB-approved research protocol, any applicable investigator brochure, and the current IRB-approved informed consent document, and b) other relevant sources of information, such as product labeling and package inserts; or
- 2) the expected natural progression of any underlying disease, disorder, or condition of the subject(s) experiencing the AE and the subject's predisposing risk factor profile for the AE.

9.4.4 Attribution

- 1) **Definite:** the AE is clearly related to the research procedures
- 2) **Probably:** the AE is likely related to the research procedures
- 3) **Possible:** the AE may be related to the research procedures
- 4) **Unlikely:** the AE is doubtfully related to the research procedures
- 5) **Unrelated:** the AE is clearly not related to the research procedures

Possibly related to participation in the research: There is a reasonable possibility that the adverse event, experience, or outcome may have been caused by the procedures involved in the research.

For each identified AE, an AE form will be completed. Reporting procedures should be started immediately (within 24 hours) upon learning of a SAE or UP.

9.4.5 Adverse Event List(s) for Commercial Agent(s) – Tamoxifen

The most common adverse events experienced with use of tamoxifen include hot flashes, night sweats, and vaginal discharge. Venous thromboembolic disease and endometrial cancer are rare risks of tamoxifen. The package inserts for tamoxifen can be found at: http://www.accessdata.fda.gov/drugsatfda_docs/label/2005/17970s053lbl.pdf

9.4.6 Interpretation of definitions

AE and UP Reporting Period

The study period during which AEs must be reported is normally defined as the period from the initiation of any study procedures to the end of the study treatment follow-up. For this study, the study treatment follow-up is defined as 14 days following the last administration of study treatment (week 25 phone call follow up).

Preexisting Condition

A preexisting condition is one that is present at the start of the study. A preexisting condition should be recorded as an AE if the frequency, intensity, or the character of the condition worsens during the study period.

General Physical Examination Findings

At screening, any clinically significant abnormality should be recorded as a preexisting condition. At the end of the study, any new clinically significant findings/abnormalities that meet the definition of an AE must also be recorded and documented as an AE.

Post-study AE

All unresolved AEs should be followed by the investigator until the events are resolved, the subject is lost to follow-up, or the AE is otherwise explained. At the last scheduled visit, the investigator should instruct each subject to report any subsequent event(s) that the subject, or the subject's personal physician, believes might reasonably be related to participation in this study. The investigator should notify the study sponsor of any death or AE occurring at any time after a subject has discontinued or terminated study participation that may reasonably be related to this study. The sponsor should also be notified if the investigator should become aware of the development of cancer or of a congenital anomaly in a subsequently conceived offspring of a subject that has participated in this study.

Abnormal Laboratory Values

A clinical laboratory abnormality should be documented as an AE if any one of the following conditions is met:

- The laboratory abnormality is not otherwise refuted by a repeat test to confirm the abnormality
- The abnormality suggests a disease and/or organ toxicity
- The abnormality is of a degree that requires active management; e.g. change of dose, discontinuation of the drug, more frequent follow-up assessments, further diagnostic investigation, etc.

Hospitalization, Prolonged Hospitalization or Surgery

Any AE that results in hospitalization or prolonged hospitalization should be documented and reported as a serious AE unless specifically instructed otherwise in this protocol. Any condition responsible for surgery should be documented as an AE if the condition meets the criteria for an AE.

Neither the condition, hospitalization, prolonged hospitalization, nor surgery are reported as an AE in the following circumstances:

- Hospitalization or prolonged hospitalization for diagnostic or elective surgical procedures for a preexisting condition. Surgery should **not** be reported as an outcome of an AE if the purpose of the surgery was elective or diagnostic and the outcome was uneventful.

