9.6 Potential risks

There are several areas of potential risk in this study. We will obtain several blood samples from each subject. There is a risk of bruising, hematoma, and infection after phlebotomy, which are possible but not considered serious AEs. Fainting may occur which is unlikely, but considered a serious AE. The removal of <71 cc of blood four times during one year is a potential risk; however this amount is routinely taken from subjects for clinical indications without adverse effect. Study medications will be delayed until after phlebotomy on each study day.

The 6MWT may cause light-headedness, chest pain, or musculoskeletal discomfort; however the risks of this study to subjects are minimal. In addition, subjects with PAH routinely undergo 6MWT for clinical indications, so this study procedure does not increase risk above usual clinical care. As subjects will be allowed to continue their other therapy, there are no alternative therapies to the ones being studied.

The risks associated with an echocardiogram are that the probe used on the chest during the echocardiogram may lead to mild soreness in the area for about a day.

For the PET scans, a radioactive drug (tracer) will be put into the body. Because the amount of radiation exposure to is small, the risk of negative effects from it is low. But the tracer itself could cause an allergic reaction, in rare instances.

The administration of tamoxifen is associated with risks, noted above.

The other risk to the subjects is the potential loss of confidentiality during data collection, although as noted above steps will be taken to maintain confidentiality completely.

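### Section 9.4.6 takes admissions for diagnostic or elective surgical procedures for a preexisting condition out of AE reporting with no limit for worsening, against its own Preexisting Condition rule and 9.4.1.2

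*Combined protocol and SAP*

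**What the plan says.** Four places in the combined protocol and SAP bear on whether an admission for a preexisting condition is recorded.

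- **9.4.6, Hospitalization, Prolonged Hospitalization or Surgery.** An AE that leads to admission is serious unless the protocol instructs otherwise. An exclusion follows: "Neither the condition, hospitalization, prolonged hospitalization, nor surgery are reported as an AE in the following circumstances". The one circumstance listed is "Hospitalization or prolonged hospitalization for diagnostic or elective surgical procedures for a preexisting condition". A further sentence keeps surgery from being reported as an AE outcome "if the purpose of the surgery was elective or diagnostic and the outcome was uneventful".
- **9.4.6, Preexisting Condition.** "A preexisting condition should be recorded as an AE if the frequency, intensity, or the character of the condition worsens during the study period".
- **9.4.1.2, Serious adverse event.** An AE that requires or prolongs a hospital stay is serious. Among the hospitalizations that are not serious are those for "routine treatment or monitoring of the studied indication, not associated with any deterioration in condition, or for elective procedures". A second exclusion covers elective or planned treatment of a pre-existing condition, on the stated condition that it has not worsened.
- **7.7 and 9.4.4.** The safety analysis summarises toxicities by incidence and grade, and safety interim analyses go to the DSMB. An AE form is completed for each identified AE, and reporting starts within 24 hours of learning of an SAE or UP.

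Two further passages touch on seriousness. Section 9.4.2 gives an example of an SAE that ends with an event that "was moderate-severe (Grade 2-3) and required or prolonged hospitalization". Section 9.6 says of phlebotomy: "Fainting may occur which is unlikely, but considered a serious AE".

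**The concern.** Section 3.2.1 requires documented PAH before entry, so PAH is a preexisting condition for all subjects. The 9.4.6 exclusion would then apply to the disease under study, and it acts at the AE level: it removes the condition as well as the admission. The 9.4.1.2 exclusions act only at the level of seriousness, and an event they exempt can still be recorded as an AE.

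Safety is a named secondary aim (2.2), and section 1.2 makes safety a paramount concern and discusses right ventricular function in that context. If staff follow the exclusion literally, some deteriorations in PAH would produce no AE form, no SAE report and no entry in the 7.7 summaries. Whether an event is recorded would depend on which paragraph was consulted.

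**Working it through.** There is no stated figure to reproduce. The check is to run the same situations through each rule.

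| Situation | Preexisting Condition (9.4.6) | 9.4.1.2 | Exclusion (9.4.6) | Consistent? |
|---|---|---|---|---|
| PAH has worsened; admitted for treatment | AE | Serious (hospital stay) | Not engaged | Yes |
| PAH has worsened; admitted for a non-surgical diagnostic procedure | AE | Serious; the studied-indication exclusion fails because of deterioration, unless the procedure counts as elective | Not an AE if diagnostic is read broadly; not engaged if it means surgery only | Only on the narrow reading |
| PAH has worsened; admitted for a diagnostic surgical procedure | AE | As in the row above | Not an AE on either reading | No |
| PAH has worsened; admitted for an elective surgical procedure | AE | Unclear: the elective-procedures clause has no worsening limit, but the separate exclusion for elective treatment does | Not an AE | No, at least for AE recording |
| PAH stable; admitted for a planned diagnostic or elective procedure | Not an AE | Not serious | Not an AE | Yes |

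Three observations follow.

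1. The general rule that a hospitalized AE is serious does not resolve the conflict. It gives way to contrary instructions elsewhere in the protocol, and the exclusion is one.
2. The 7.7 summaries do not recover the event, because they are built from recorded events and the exclusion stops the recording.
3. The narrow reading of *diagnostic* resolves the second row only. In the third and fourth rows a worsened condition is still left unreported, contrary to the Preexisting Condition paragraph.

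**Scale.** Inputs: 12 subjects per arm (abstract and 7.4). One subject's event recorded or not changes an arm's proportion by 1/12 = 0.083, or 8.3 percentage points. Section 7.4 replaces dropouts so that at least 12 complete in each arm, so the safety denominator may exceed 12 and the step would then be smaller. The documents give no frequency for procedure admissions, so the expected number of affected events cannot be computed.

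**Two smaller misalignments.** The 9.4.2 example attaches *disabling* to Grade 4, while the scale just above it describes Grade 3 as "disabling; limiting to self-care ADL"; the example also leaves out important medical events. The 9.6 sentence treats a phlebotomy faint as serious without condition, whereas under 9.4.1.2 it would be serious only if it met a listed criterion or was judged an important medical event.

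**The case against.** The best defence is that the exclusion is meant for surgery. The word *surgical* can govern both *diagnostic* and *elective*, and the sentence that follows speaks of surgery done for either purpose. On that reading ordinary diagnostic work-up is not excluded. Admission to treat worsening PAH is an SAE in any case, and the AE definition in 9.4.1.1 already covers worsening. The elective-procedures clause in 9.4.1.2 has no worsening limit either, so the contrast between sections is not perfectly clean. Right ventricular function is also measured by echocardiography at baseline, Week 12 and Week 24, whatever is coded as an AE.

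Most of this stands, and it limits the reach of the point. It does not remove it. The surgical-only reading is plausible but not stated, and under it the exclusion still suppresses a worsened condition. Scheduled echocardiography measures an endpoint; it does not fill the AE listing or prompt expedited reporting.

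A reader might infer something stronger from 9.4.2: that it narrows SAEs to Grade 4, Grade 5 or hospitalized events, so that a thromboembolic event managed without admission could go uncounted. The documents do not support this. The sentence is offered as an example, directly after a statement that severity and seriousness differ. Section 9.4.1.2 keeps important medical events as a criterion and illustrates it with events that did not lead to admission. Such a thromboembolic event can therefore be an SAE, and it is an AE in any case, within the incidence and grade summaries of 7.7.

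**Conclusion.** The point holds as a conflict of wording with a real but limited consequence. Read literally, the 9.4.6 exclusion drops worsening PAH from AE and SAE recording when the admission is for a procedure it covers. The Preexisting Condition paragraph makes the same worsening an AE, and 9.4.1.2 makes the admission serious unless its elective-procedures clause applies. The gap covers procedure admissions only, and its width depends on how *diagnostic* is read.

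The size per affected subject is at most 8.3 percentage points of an arm's event proportion, assuming 12 or more subjects in the arm. The number affected is unknown. A reader might also infer a bias between arms. Study personnel are masked (4.5), and nothing in the documents shows that the omission would act differently by arm, so the supported conclusion is possible under-recording. The primary TAPSE analysis is not affected. The 9.4.2 and 9.6 points are secondary alignments.

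**What to change.** 1. In the 9.4.6 exclusion, add a condition such as: *provided the preexisting condition has not worsened since baseline*.
2. State in the same place whether *diagnostic* covers non-surgical procedures.
3. State that 9.4.1.2 is the controlling test of seriousness, and clarify there whether its elective-procedures clause applies when the condition has deteriorated.
4. Align the 9.4.2 example with its own grading scale and with 9.4.1.2, including important medical events, or delete it.
5. Reconcile the fainting sentence in 9.6 with 9.4.1.2.

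These are wording edits plus a short note to the staff who record events, with no effect on design or sample size. The one downside is that slightly more admissions with worsening PAH will be recorded as AEs or SAEs.
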